3.7 Sample Size

Study 1

G*power was utilized for sample size calculation with equal group sizes (i.e ratio of groups 1:1). A total of 36 participants with CAI (i.e. 18 in each group) to be able to reject the null hypothesis that the population means of the experimental and control groups are equal with probability (power) 0.95. The Type I error probability associated with this test of this null hypothesis is 0.05¹¹.

- Assuming a total drop-out rate of 10%, we will recruit 20 subjects for each group, i.e. 20 experimental and 20 experimental control group.

Study 2

A total of 20 participants without CAI will be recruited and compared with the age matched CAI participants in the study 1.

4. Statistical Analysis Plan (SAP)

All Studies

Descriptive and inferential statistics will be used. Normally distributed data will be presented by mean and standard deviation (SD) and non-normally distributed data will be presented by median and interquartile range. Categorical data will be presented using percentages. SPSS (version 22.0) will be used for all statistical analyses.

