3.2 Participants

Study 1 and 2

University students those who involved in collegial sports with chronic ankle instability and without chronic ankle instability/musculoskeletal injuries from INTI International University at Malaysia will be eligible to participate in this study.

Study investigators will not be eligible to participate.

Participants randomized to experimental group in the study 1 will require a personal android support hand phone to the install the VAMDB from the google app store to participate.

3.3Recruitment

Study 1

All participants with chronic ankle instability (CAI) attending the INTI physiotherapy centre will be enrolled in the study at Phase 1. The participation information and consent sheet will be distributed which details including inclusion and exclusion criteria. Interested CAI participants will be invited to undergo baseline assessments (pain – Visual analog score (VAS), Brief pain inventory (BPI); Balance – Cumberland ankle instability tool (CAIT), functional ankle disability index (FADI) and Y-balance test; psychology – mindfulness attention awareness score (MAAS) and oxford happiness questionnaire (OHQ); quantitative EEG) with scheduled appointments.

All participants will have to return a signed consent form to the physiotherapy centre officer to random allocation to a study group.

Study 2

All participants without chronic ankle instability (CAI)/ musculoskeletal injuries will be invited by flyers and sending an invitation to University sports club. The participation information and consent sheet will be distributed which details including inclusion and exclusion criteria. Interested CAI participants will be invited to undergo baseline

assessments (Balance – Cumberland ankle instability tool, functional ankle disability index; psychology – mindfulness attention awareness score and oxford happiness questionnaire; quantitative EEG) with scheduled appointments. All participants will have to return a signed consent form to physiotherapy centre officer for allocation to a study group

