3.5 Administration

Study 1

Participants allocated to experimental and experimental control group will be given the appropriate access for 12 weeks (instructions provided in the study envelope). Participants will be encouraged to attend the regular appointments for 5 times a week for 6 weeks intervention and follow up (week12) in INTI international university physiotherapy centre. At

the end of week 3, end of week 6 and end of week 12 instructed to participate in post intervention assessments the duration of waiting time and assessment time will be clearly stated under the guidelines.

Study 2

Participants allocated to healthy control group will be given the appropriate access for baseline assessment (instructions provided in the study envelope)

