4.1 Primary Outcomes

Study 1

The primary analyses will compare: (1) experimental vs experimental control group guidelines on their mean and standard deviation: (i) pain score (VAS & BPI), (ii) balance scores (CAIT & FADI), (iii) mindful attention (MAAS), and (iv) happiness scores (OHQ). Comparisons will be made using an unpaired t-test or a Mann-Whitney test for parametric and non-parametric data, respectively. P-values <0.05 will be considered statistically significant.

2*4-Repeated measures analysis of variance (ANOVA) will be performed to test the significant difference in the intervention effects between the time intervals (baseline, mid-intervention, post-intervention, and follow-up) and also between the two groups (Experimental control group and Experimental Group).

The post-hoc analysis will be conducted to investigate significant effect within the time intervals. Condition on if the sphericity violated (p-value < 0.05), the Greenhouse- Geisser estimated correction will be applied.

Effect sizes for will be calculated using Cohen's d (d) with 95% confidence intervals (95%CI) using the 'effsize' package¹². Effect sizes will be considered small if $0.2 \leq d < 0.5$, medium if $0.5 \leq d < 0.8$, and large if $d \geq 0.8$.

Study 2

The primary analyses will compare: (1) CAI participants vs healthy control group guidelines on their mean and standard deviation: (i) balance scores (CAIT &FADI) (ii), mindful attention (MAAS) and (iii) happiness scores (OHQ). Comparisons will be made using an unpaired t-test or a Mann-Whitney test for parametric and non-parametric data, respectively. P-values <0.05 will be considered statistically significant.

Effect sizes for will be calculated using Cohen's d (d) with 95% confidence intervals (95%CI) using the 'effsize' package¹². Effect sizes will be considered small if $0.2 \leq d < 0.5$, medium if $0.5 \leq d < 0.8$, and large if $d \geq 0.8$.

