4.3 Missing Data

For participants who are randomized and do not attend for assessment, a mean imputation of the assessment scores from their allocation group will used.

5. Informed Consent Forms (ICF)

Study 1

Written consent will be gained from the study participants with CAI using the consent forms attached to the application.

Study 2

Written consent will be gained from the study participants without CAI using the consent forms attached to the application.

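### The main group comparison in 4.1 ignores a baseline score already collected, 4.3's group-mean imputation lifts its error rate to about 0.08, and the 0.95 power in 3.7 has no stated effect size

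*Protocol*

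**What the plan says.** Protocol 3.7 (Sample Size, Study 1) reports a G*Power calculation with 1:1 allocation: 18 per group "to be able to reject the null hypothesis that the population means of the experimental and control groups are equal with probability (power) 0.95", at a type I error of 0.05. A 10% drop-out allowance brings recruitment to 20 per group. It gives no effect size, SD, outcome, visit, test or sidedness. Section 3.6 lists seven primary instruments.

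For the primary comparison of the two arms, 4.1 says: "Comparisons will be made using an unpaired t-test or a Mann-Whitney test for parametric and non-parametric data, respectively". It adds: "P-values <0.05 will be considered statistically significant". A second analysis follows: "2*4-Repeated measures analysis of variance (ANOVA) will be performed to test the significant difference in the intervention effects between the time intervals", with baseline as one of its four times. The same section labels effects for reporting, "and large if $d \geq 0.8".

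Section 3.3 describes baseline assessment ahead of random allocation: "Interested CAI participants will be invited to undergo baseline assessments". Section 3.5 sets three later assessments: "end of week 3, end of week 6 and end of week 12 instructed to participate in post intervention assessments". For randomised participants who do not attend an assessment, 4.3 prescribes "a mean imputation of the assessment scores from their allocation group will used".

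**The concern.** Three statements that should fit together do not.

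- A power of 0.95 means nothing until the effect is given. A reader of a null result would take it as backed by 95% power without knowing against what difference.
- The test that 4.1 uses for the primary comparison makes no use of the baseline score, although every randomised participant should have one. In a trial of 18 evaluable per arm, that gives up precision that costs nothing to recover.
- Filling gaps with the participant's own group mean adds apparent sample size and removes spread, so the 0.05 level in 3.7 and 4.1 is not the level at which the t-test operates once visits are missed.

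**Working it through.** **Inputs from the protocol.** 18 evaluable and 20 recruited per arm, 10% drop-out, alpha 0.05, power 0.95 (3.7); tests and the 0.8 threshold (4.1); three post-baseline visits (3.5). **Assumed, because not stated:** two-sided testing; a correlation r of 0.3, 0.5 or 0.7 between baseline and follow-up; for the 2x4 ANOVA, the same r between all pairs of visits. Effects d are in SD units.

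**1. The plan's own figures.** Drop-out: 18/0.9 = 20, which reproduces. The 0.95 cannot be recomputed directly, so it is solved backwards. For the t-test, the noncentrality is d x sqrt(18/2) = 3d with 34 df and critical value 2.032. Power 0.95 needs d = 1.237 (one-sided: 1.12). Two settings lead to 36 participants:
- t-test at d = 1.25: 17 per arm gives 0.942, 18 per arm gives 0.954.
- Group-by-time interaction at f = 0.25, r = 0.5: noncentrality f² x N x 4/(1 − r) = 0.0625 x 36 x 4/0.5 = 18 on 3 and 102 df, power 0.952. N = 34 gives 0.939.

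The protocol states neither.

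**2. t-test.** At d = 0.8 the noncentrality is 2.4 and power 0.645. At d = 0.5 it is 1.5 and power 0.308.

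**3. ANCOVA at one visit.** Adjustment leaves residual variance 1 − r², so the noncentrality is 3d/sqrt(1 − r²) on 33 df. At d = 0.8, r = 0.5: 2.4/0.866 = 2.77, power 0.767. Over the three correlations this gives 0.685/0.767/0.903. That assumes exactly balanced baselines. Chance imbalance divides the noncentrality by sqrt(1 + t²/34), where t is the baseline t statistic. Averaging over its distribution gives 0.672/0.755/0.895, and simulation agrees. These lower figures are the ones used here.

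**4. 2x4 interaction.** Noncentrality is (18/2) x S/(1 − r), where S is the sum of squared deviations of the four group differences from their mean.
- Equal effect at weeks 3, 6 and 12: S = 0.75d² = 0.48, so 4.32/(1 − r) = 6.17/8.64/14.40.
- Half the effect at weeks 3 and 12: S = 0.5d² = 0.32, so 2.88/(1 − r) = 4.11/5.76/9.60.

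| Power, 18 observed per arm | r = 0.3 | r = 0.5 | r = 0.7 |
|---|---|---|---|
| t-test, d = 0.8 | 0.645 | 0.645 | 0.645 |
| ANCOVA, d = 0.8 | 0.672 | 0.755 | 0.895 |
| Interaction, d = 0.8, equal effect | 0.514 | 0.673 | 0.893 |
| Interaction, d = 0.8, half effect at weeks 3 and 12 | 0.355 | 0.483 | 0.724 |
| t-test, d = 0.5 | 0.308 | 0.308 | 0.308 |
| ANCOVA, d = 0.5 | 0.325 | 0.38 | 0.52 |

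**5. Group-mean imputation.** With 18 observed and 2 imputed per arm, the means and the within-group sum of squares do not change. The df rise from 34 to 38 and the nominal n from 18 to 20. The t statistic is therefore multiplied by sqrt(38/34) x sqrt(20/18) = 1.114. The critical value on 38 df, 2.024, corresponds to 2.024/1.114 = 1.817 on the honest scale. With 34 df that is exceeded under the null with probability 0.078. With one missing per arm the result is 0.063; with none, 0.05. Simulation gives 0.077 to 0.078 for ANCOVA on the imputed data as well, so adjustment alone does not cure this.

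**The case against.** **The 0.95 may be right.** This stands. A reader might infer that the sample size is miscalculated or that the trial is shown to be underpowered. The document does not support that: 36 fits an interaction test at f = 0.25, r = 0.5, and a t-test at d = 1.25. The null described in 3.7, equal population means in the two groups, is not the interaction null, so that origin is conjecture. The fault is an undisclosed basis.

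**The plan does use baseline.** Also true in part. The 2x4 interaction compares change from baseline, so it would be wrong to say that 4.1 discards baseline altogether. At r = 0.7 with an equal effect at all visits, it matches one-visit ANCOVA (both 89% before rounding up). It falls behind at lower correlations or when the effect varies over time. The missing covariate is lost efficiency, not an error of validity.

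**The gain rests on assumed inputs.** It does. The protocol gives no r, and its 0.8 is a reporting label, not a design effect. At r = 0.3 the gain over the t-test is only about 3 points at d = 0.8 and 2 at d = 0.5.

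**One-visit ANCOVA leaves two visits unused.** Fair. ANCOVA on the mean of the three visits would give about 93/94/98% at d = 0.8 if the effect were equal throughout. That depends on a constant effect; a single named visit does not.

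**Imputation is a separate matter.** It is a different mechanism and its size depends on how many visits are missed. It belongs here because it acts on the same test and breaks the 0.05 to which the power statement is tied.

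**Conclusion.** The point holds in three parts of unequal strength.

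- **Wrong as written:** at the protocol's own 10% drop-out, 4.3 moves the t-test's type I error from 0.05 to about 0.08. This assumes two per arm missing for reasons unrelated to the score.
- **Improvable at no data cost:** baseline adjustment takes power at 0.8 SD from 65% to about 67/76/90%, and at 0.5 SD from 31% to about 33/38/52%, for r = 0.3/0.5/0.7. Sidedness and r are assumptions, and the figures are per score, with no allowance for testing several primary scores.
- **Incomplete:** on the t-test in 4.1, 95% power holds only for d of about 1.24, well above the protocol's threshold for a large effect. ANCOVA does not rescue the 0.95 at 0.8 SD over the range of r considered.

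This should be fixed, but it does not call for a larger trial.

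**What to change.** 1. **Section 4.1.** For each primary score, make the main between-group comparison an ANCOVA of the score at one post-baseline visit named in advance (for example end of week 6, post-intervention), with group as factor and baseline score as covariate, two-sided 0.05. Keep the t-test, Mann-Whitney test and 2x4 ANOVA as supporting analyses.
2. **Section 4.3.** State that this comparison uses observed scores at the named visit and not the group-mean imputation.
3. **Section 3.7.** Restate the power for that test with its outcome, visit, sidedness and effect size, for example: 18 observed per arm, about 67 to 90% at 0.8 SD for an assumed correlation of 0.3 to 0.7. If the t-test stays as the main test, say that 95% holds only at d of about 1.24, with 65% at 0.8. If the interaction was the basis, give f, r and the effect assumed at each visit.

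Keep N at 40. No participants, visits or measurements are added. The costs are a changed primary test, the loss from it of anyone who misses the named visit (which assumes that missingness depends only on group and baseline), and a stated power less favourable than 0.95. The change must be fixed before outcome data are seen.

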4.1 Primary Outcomes

Study 1

The primary analyses will compare: (1) experimental vs experimental control group guidelines on their mean and standard deviation: (i) pain score (VAS & BPI), (ii) balance scores (CAIT & FADI), (iii) mindful attention (MAAS), and (iv) happiness scores (OHQ). Comparisons will be made using an unpaired t-test or a Mann-Whitney test for parametric and non-parametric data, respectively. P-values <0.05 will be considered statistically significant.

2*4-Repeated measures analysis of variance (ANOVA) will be performed to test the significant difference in the intervention effects between the time intervals (baseline, mid-intervention, post-intervention, and follow-up) and also between the two groups (Experimental control group and Experimental Group).

The post-hoc analysis will be conducted to investigate significant effect within the time intervals. Condition on if the sphericity violated (p-value < 0.05), the Greenhouse- Geisser estimated correction will be applied.

Effect sizes for will be calculated using Cohen's d (d) with 95% confidence intervals (95%CI) using the 'effsize' package¹². Effect sizes will be considered small if $0.2 \leq d < 0.5$, medium if $0.5 \leq d < 0.8$, and large if $d \geq 0.8$.

Study 2

The primary analyses will compare: (1) CAI participants vs healthy control group guidelines on their mean and standard deviation: (i) balance scores (CAIT &FADI) (ii), mindful attention (MAAS) and (iii) happiness scores (OHQ). Comparisons will be made using an unpaired t-test or a Mann-Whitney test for parametric and non-parametric data, respectively. P-values <0.05 will be considered statistically significant.

Effect sizes for will be calculated using Cohen's d (d) with 95% confidence intervals (95%CI) using the 'effsize' package¹². Effect sizes will be considered small if $0.2 \leq d < 0.5$, medium if $0.5 \leq d < 0.8$, and large if $d \geq 0.8$.

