3.6 Assessment & Outcomes Measures

Study 1

Chronic ankle Instability (CAI) participants will be assessed for:

1. Primary outcomes
 - Cumberland Ankle Instability Tool (CAIT)
 - Ankle stability will be assessed by validated 9-item Questionnaire, to find the chronic ankle disability score among participants and to recruit in the study if the score was ≤ 27 in the CAIT tool over 30.
 - Y-balance test (YBT)
 - The dynamic balance of the participants will be assessed using reliable and validated the Y balance test (YBT) by measuring the distance in anterior, posterolateral, and posteromedial directions.
 - Visual analog scale (VAS)
 - CAI participants pain intensity will be record by self-reported pain intensity on a 10 cm line to point out the pain level. The point at 0 cm represents "no pain" and 10 cm represents "worst pain".
 - Brief Pain Inventory (BPI)

- Besides VAS, pain intensity and pain interference will be recorded using 4-items (worst pain, least pain, average pain, and pain right now) to measure the pain intensity, and 7-items (general activity, mood, walking, normal work, relations, sleep, enjoyment of life) to assess the pain interference. The participants will be instructed to report the pain intensity from 0 (no pain) to 10 (as pain bad as you can imagine). Similarly, the pain interference is recorded from 0 (does not interfere) to 10 (completely interferes)
- Mindful Attention Awareness Scale (MAAS)
 - CAI participants will be assessed by 15-item questionnaire to identify the participants' mindfulness level during the ankle instability.
- Oxford Happiness Questionnaire (OHQ)
 - Happiness level of CAI participants will be assessed using the Oxford Happiness Questionnaire (OHQ), which consists of a 29-item questionnaire.
- Functional ankle disability index (FADI)
 - CAI participants will be asked to complete 34-item questionnaire used to check the participant's general daily activity and sports specific functions for physical function and disability.

2. Secondary outcomes

- Non-invasive wireless electroencephalogram (EEG)
 - EEG will be used at 14 positions: AF3, AF4, F3, F4, F7, F8, FC5, FC6, P7, P8, T7, T8, O1, and O2. The EEG recordings of the CAI participants will be collected between 9 and 12 hours in the morning to reduce participants sleeping artifacts and to exclude the EEG from the influence of circadian variables. The EEG recordings will be recorded in eyes closed and eyes

open for 2mins.

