4.2. Secondary Outcomes

Study 1

The primary analyses will compare: (1) experimental vs experimental control guidelines on their mean and standard deviation of brain waves (alpha, beta, theta, gamma and delta).

Comparisons will be made using an unpaired t-test or a Mann-Whitney test for parametric and non-parametric data, respectively. P-values <0.05 will be considered statistically significant.

2×4-Repeated measures analysis of variance (ANOVA) will be performed to test the significant difference in the intervention effects between the time intervals (baseline, mid-intervention, post-intervention, and follow-up) and also between the two groups (Experimental control group and Experimental Group).

The post-hoc analysis will be conducted to investigate significant effect within the time intervals. Condition on if the sphericity violated (p-value < 0.05), the Greenhouse- Geisser estimated correction will be applied.

Effect sizes for will be calculated using Cohen's d (d) with 95% confidence intervals (95%CI) using the 'effsize' package. Effect sizes will be considered small if $0.2 \leq d < 0.5$, medium if $0.5 \leq d < 0.8$, and large if $d \geq 0.8$.

Study 2

The primary analyses will compare: (1) CAI participants vs healthy control group guidelines on their mean and standard deviation brain waves (alpha, beta, theta, gamma and delta).

Comparisons will be made using an unpaired t-test or a Mann-Whitney test for parametric and non-parametric data, respectively. P-values <0.05 will be considered statistically

significant.

Effect sizes for will be calculated using Cohen's d (d) with 95% confidence intervals (95%CI) using the 'effsize' package. Effect sizes will be considered small if $0.2 \leq d < 0.5$, medium if $0.5 \leq d < 0.8$, and large if $d \geq 0.8$.

Pearson's correlation or a spearman's correlation for parametric and non-parametric data, respectively will be used to report the association of EEG with the primary outcomes pain intensity (VAS &BPI) and pain interference (BPI).

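### Study 1 has seven primary outcomes in section 3.6 but six in the group comparison of 4.1, each tested at an unadjusted 0.05 with no ranking or success rule, so no overall error rate is controlled

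*Protocol*

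**What the plan says.** Section 3.6 places seven instruments under the Study 1 primary outcomes: CAIT, Y-balance, VAS, BPI, MAAS, OHQ and FADI. The Y-balance entry reads "The dynamic balance of the participants will be assessed using reliable and validated the Y balance test (YBT") and gives three reach directions.

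Section 4.1 then defines the primary group comparison. After the pain scores (VAS and BPI) it continues ("ii) balance scores (CAIT & FADI), (iii) mindful attention (MAAS), and (iv) happiness scores (OHQ"), six outcomes in all, compared by an unpaired t-test or a Mann-Whitney test. The decision rule is "P-values <0.05 will be considered statistically significant". The section adds: "2*4-Repeated measures analysis of variance (ANOVA) will be performed to test the significant difference in the intervention effects between the time intervals". That paragraph lists four time points but no outcomes. The only correction mentioned is Greenhouse-Geisser.

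Section 3.7 sizes Study 1 at 36 participants to "reject the null hypothesis that the population means of the experimental and control groups are equal with probability (power) 0.95", with a type I error of 0.05 for that one test. It names no outcome, effect size or test family.

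Section 3.3 groups "functional ankle disability index (FADI) and Y-balance test" with CAIT under balance. Section 3.5 schedules assessments after baseline at the ends of weeks 3, 6 and 12. Section 4.2 refers to "primary outcomes pain intensity (VAS &BPI) and pain interference (BPI"), which treats BPI as two separate scores.

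**The concern.** There are two linked faults.

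First, the lists of primary outcomes disagree. Y-balance is primary in 3.6 and a balance measure in 3.3, but in 4.1 the balance scores are CAIT and FADI only, and chapter 4 does not name Y-balance at all. An outcome called primary therefore has no stated two-group analysis.

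Second, 4.1 gives six outcomes equal primary standing and an unadjusted threshold each. Section 3.7 attaches its error rate and power to one hypothesis. Nothing connects the two: no single or ranked outcome, no primary visit for the two-group tests, no statement of whether one, some or all outcomes must be significant, and no adjustment. As written, a single significant result out of six or seven could be presented as the trial's positive primary finding, and the reader could not tell from the plan whether that was the intended test.

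**Working it through.** **Inputs from the protocol.** Per-test threshold 0.05 (4.1); number of primary outcomes k = 6 (4.1) or k = 7 (3.6); 18 per arm for the calculation, 20 per arm recruited; power 0.95 (3.7).

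**Assumed, because the protocol does not give them.** Two-sided tests; one test per outcome at one visit; the correlations between outcomes; any one p<0.05 read as success.

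**The plan's own figure.** The dropout step reproduces: 36 / (1 − 0.10) = 40, or 20 per arm. The 36 cannot be reproduced without an effect size, so it was solved backwards:
- Two-sided t-test, 18 per arm, alpha 0.05, power 95%: d = 1.24 (noncentrality 1.237 × √(18/2) = 3.71 on 34 degrees of freedom).
- Group-by-time F test in a 2×4 design, with assumed f = 0.25, correlation 0.5 and sphericity: noncentrality 0.25² × 36 × 4 / (1 − 0.5) = 18 on 3 and 102 degrees of freedom, power 95.2%. At N = 34 the power is 93.9%, so 36 is the smallest even total reaching 95%.

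Both readings fit 36, and both are one test at 0.05.

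**False-positive risk, independent outcomes.** 1 − (1 − 0.05)^k:
- k = 6: 1 − 0.95^6 = 26.5%
- k = 7: 1 − 0.95^7 = 30.2%

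**False-positive risk, correlated outcomes.** These come from 60,000 simulated trials with multivariate normal outcomes, 20 per arm, two-sided t-tests and no true difference on any outcome. The figures are the chance of at least one p<0.05.

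| Common correlation | 0 | 0.3 | 0.5 | 0.7 | 0.8 |
|---|---|---|---|---|---|
| Six outcomes | 26.2% | 24.1% | 20.9% | 16.6% | 14.0% |
| Seven outcomes | 30.0% | 27.4% | 23.1% | 18.1% | 15.0% |

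With mixed correlations (VAS–BPI 0.8, CAIT–FADI 0.7, MAAS–OHQ 0.5, other pairs 0.3) the risk is 22.3% for six and 25.2% for seven. With 18 per arm every figure is within 0.5 points. Testing each outcome at 0.05/k in the same simulations gives 2.7–5.0%.

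**Power at the first Holm step for one pre-picked outcome, 18 per arm.**
- t-test, d = 1.237: 95.0% at 0.05; 81.1% at 0.05/6 = 0.0083; 79.4% at 0.05/7 = 0.0071.
- Interaction F test as above: 95.2% at 0.05; 83.3% at 0.05/6; 81.9% at 0.05/7.

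**Power for at least one correct rejection under Holm.** These come from 30,000 simulated trials, 18 per arm, d = 1.237 on the responding outcomes and 0 on the rest. Ranges run from correlation 0.8 to 0.3.

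| Outcomes that respond | Of six | Of seven |
|---|---|---|
| One | 81% | 79% |
| Two | 88–94% | 87–93% |
| Three | 91–98% | 90–97% |
| All | 94% to above 99% | 94% to above 99% |

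**The case against.** - **The 0.05 in 3.7 is a per-test rate, and each test in 4.1 keeps it.** This is correct. What is uncontrolled is the rate across the set. But 3.7 describes one test and 4.1 runs at least six with equal primary status, so the stated 5% does not describe the chance of a false primary claim.
- **The inflation needs a success rule that the plan does not state.** This also stands, as a condition on the size. If all outcomes had to be significant, alpha would need no adjustment. Power would then be 0.95^6 = 74% or 0.95^7 = 70% for independent outcomes each powered at 95%. Section 4.1 states neither rule.
- **The four domains might be four separate questions.** The text does not say so, and pain and balance each still hold two outcomes.
- **The ANOVA may cover Y-balance or act as a gatekeeper.** It names no outcomes, and the two-group tests are not made conditional on it. Greenhouse-Geisser deals with sphericity within an outcome, not with multiplicity across outcomes.
- **These details could sit in a separate analysis plan.** That has some force for the visit and the success rule. It does not for the threshold or the outcome lists: chapter 4 is itself headed "Statistical Analysis Plan (SAP") and fixes the threshold, and the two lists conflict within this one document.
- **Zero correlation is a ceiling only with one score per outcome.** This stands. With two BPI scores and three Y-balance directions, 3.6 gives 5 + 2 + 3 = 10 tests, and 1 − 0.95^10 = 40%.

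**Conclusion.** The concern holds and must be fixed. The disagreement between 3.6 and 4.1 over Y-balance is plain from the text and rests on no assumption. So does the absence of any ranking, success rule or adjustment beside the unadjusted 0.05.

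The size is conditional. If any one significant outcome counts as success, the risk of a false primary claim is roughly three to six times 5%. Positive correlation is likely, since VAS overlaps with BPI and CAIT with FADI, so values below the independence figures are more realistic; the mixed-correlation case gives 22% and 25%. Repeating the two-group tests at several visits, which the plan neither states nor rules out, would raise the risk further. The correlations, d and f are assumptions, not figures from the protocol.

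**What to change.** Use the same primary list in 3.6 and 4.1. Either give Y-balance one defined score and a stated primary analysis, or make it secondary. Then choose one of two routes.

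- **(a) Preferred.** The sponsor names one primary outcome (one score), one visit and one test, and all other outcomes and visits become secondary. Alpha stays at 0.05 with no increase in sample size. The cost is a narrower base of primary evidence.
- **(b)** Keep several primaries, each with one score (for BPI, intensity or interference), one visit and one model, under Holm's procedure at an overall two-sided 0.05, with success defined as at least one rejection. The cost is power: for a single pre-picked outcome at the first step it falls from 95% to about 79–83%, depending on the test and the number of outcomes. Power for at least one rejection depends on how many outcomes respond.

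In both cases, state in 3.7 which outcome, effect size and test the 36 participants and 95% power refer to, and under (b) restate the power. The changes are to wording in 3.6, 3.7 and 4.1; no extra enrolment is proposed.

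### The 2×4 ANOVA counts baseline as an outcome visit and does not say which term tests treatment; its group test is valid but diluted to 0.75 of a constant effect

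*Protocol*

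**What the plan says.** Protocol section 4.1 (Study 1) sets out two analyses.

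- **Two-sample comparison of the arms.** "Comparisons will be made using an unpaired t-test or a Mann-Whitney test for parametric and non-parametric data, respectively". Neither a visit nor a baseline adjustment is given.
- **2×4 repeated-measures ANOVA.** The "ANOVA) will be performed to test the significant difference in the intervention effects between the time intervals", these being "baseline, mid-intervention, post-intervention, and follow-up", "and also between the two groups (Experimental control group and Experimental Group"). The follow-up step is: "The post-hoc analysis will be conducted to investigate significant effect within the time intervals".

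Section 4.2 repeats the ANOVA wording for the EEG outcomes: "2×4-Repeated measures analysis of variance (ANOVA) will be performed to test the significant difference in the intervention effects between the time intervals". Neither section mentions a group-by-time interaction, a between-arm contrast of change, or baseline as a covariate.

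Three other places matter. Section 3.4 gives standard physiotherapy to both randomised arms, with the breathing exercise added in one. Section 3.5 places the later assessments at the ends of weeks 3, 6 and 12. Section 3.7 sizes the trial: "A total of 36 participants with CAI (i.e. 18 in each group"), testing that the "population means of the experimental and control groups are equal with probability (power) 0.95".

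**The concern.** The trial asks whether adding mindful breathing to physiotherapy does better than physiotherapy alone. A 2×4 ANOVA yields three terms, and they answer different questions.

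- **Time** asks whether participants as a whole changed. Both arms are treated, so both may improve with no benefit from the addition.
- **Group** compares the arms on the average of all four visits. One of those visits precedes treatment, where no effect can exist, so the estimate is diluted. It also carries a quarter of any chance baseline difference.
- **Group by time** asks whether the arms changed differently. The plan does not name it.

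The treatment test is therefore not identified. The between-arm term that is named uses the baseline measurement to weaken the comparison, when the same measurement could sharpen it. In a trial of 36 evaluable participants that loss is material.

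**Working it through.** **Inputs from the Protocol.** 18 per arm, alpha 0.05, power 0.95 (section 3.7); four visits including baseline (section 4.1).

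**Assumptions.** The Protocol gives no effect size, SD, visit correlation or sidedness. I take two-sided tests, unit SD at each visit, equal correlation ρ of 0.3, 0.5 or 0.7 between visits, no difference at baseline, and a constant difference d at weeks 3, 6 and 12. The main case is d = 0.8.

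**The plan's own figure.** The 36 cannot be reproduced without an effect size. Solved backwards, 18 per arm gives 95% power for a two-sample t-test at d = 1.24 (1.12 if one-sided).

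**Step 1, group main effect.** The expected difference is (0 + d + d + d)/4 = 0.75d. The variance of a participant's four-visit mean is (1 + 3ρ)/4. At ρ = 0.5 this is 0.625, so the non-centrality is 0.6/√(2 × 0.625/18) = 2.28 on 34 df, and power is 60%.

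**Step 2, baseline-adjusted mean of weeks 3, 6 and 12.** The expected difference is d. The variance after adjustment is (1 + 2ρ)/3 − ρ². At ρ = 0.5 this is 0.6667 − 0.25 = 0.4167, so the non-centrality is 0.8/√(2 × 0.4167/18) = 3.72 on 33 df, and power is 95%.

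**Step 3, relative efficiency.** [0.75²/((1 + 3ρ)/4)] × [(1 + 2ρ)/3 − ρ²]. At ρ = 0.5: 0.9 × 0.4167 = 0.375.

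**Step 4, interaction F in the four-level ANOVA.** Non-centrality is (18/2) × 0.75d²/(1 − ρ) = 4.32/(1 − ρ) at d = 0.8, on 3 and 102 df.

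**Step 5, unpaired t-test at one post-baseline visit.** Non-centrality is 0.8 × √(18/2) = 2.40 on 34 df.

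| d = 0.8, 18 per arm | ρ = 0.3 | ρ = 0.5 | ρ = 0.7 |
|---|---|---|---|
| Group main effect, four visits | 72% | 60% | 51% |
| Group-by-time interaction | 51% | 67% | 89% |
| Unpaired t-test, one visit | 65% | 65% | 65% |
| Baseline-adjusted post-baseline mean | 94% | 95% | 99% |
| Efficiency, row 1 against row 4 | 52.5% | 37.5% | 22.5% |

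**Step 6, other effect sizes.** The efficiency ratio does not depend on d, but the power gap does. At d = 0.5 the group main effect has 36/28/24% power against 59/62/74% for the adjusted contrast. At d = 1.24 it has 98/93/87%, so the loss is small if the effect is that large.

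**Step 7, the time test.** Suppose there is no treatment effect and both arms improve by 0.5 SD after baseline. Non-centrality is 36 × 0.75 × 0.25/(1 − ρ) = 6.75/(1 − ρ), and the time test rejects in 73/87/98% of trials. That is correct detection of a real change over time, so it is not an error rate. It does show that the term carries no information about the added breathing. In a simulation at ρ = 0.5 with no treatment effect and both arms improving by 0.8 SD, the time test rejected in 99.9% of runs, the group test in 4.7% and the interaction in 4.5%.

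**The case against.** **The arms are compared directly elsewhere.** This stands. The two-sample test in section 4.1 is introduced as the primary comparison and sets one randomised arm against the other. The defect lies in the ANOVA and does not extend to every planned analysis. That test still names no visit and makes no use of baseline.

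**The group main effect is a proper randomised test.** This also stands. It rejected in about 5% of simulated null trials. A reader might infer that nothing in the ANOVA tests treatment; that goes too far, because the group term does so with a diluted estimate. At a correlation of 0.3 it has more power than the interaction (72% against 51%).

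**The wording may already mean the interaction.** Effects of intervention that differ between times and between groups could be loose language for the full factorial, and software prints the term. The text does not exclude this. Nor does it name the interaction as the test of interest, so the choice stays open until results are seen.

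**The post-hoc wording need not mean change within each arm.** It could mean visit-to-visit contrasts, or arm comparisons at each visit. A reader might infer that the plan will run separate paired tests per arm and claim benefit when only one is significant. With no treatment effect, both arms improving by 0.5 SD and ρ = 0.5, each such test has power 0.516, so exactly one would be significant in 2 × 0.516 × 0.484 = 50% of trials. The Protocol plans no such tests, so this figure does not describe the plan. Regression to the mean after selection on a low CAIT score likewise matters only for within-arm change, and falls on both arms alike.

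**A separate SAP may settle it.** Possibly, but section 4 of the Protocol carries that title itself and fixes these tests.

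**Conclusion.** The concern holds in a limited form. The ANOVA in sections 4.1 and 4.2 does not identify its treatment test. Its time term cannot answer the treatment question, and its group term is valid but estimates only 0.75 of a constant post-baseline effect. Against a baseline-adjusted contrast from the same data, the group term is 52.5/37.5/22.5% efficient at correlations of 0.3/0.5/0.7. At d = 0.8 its power is 72/60/51% instead of 94/95/99%.

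These sizes rest on an assumed effect, equal correlations and an effect that is constant after baseline. If only half the effect is present at week 3, the group term estimates (0 + 0.5 + 1 + 1)/4 = 0.625 of d.

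Two stronger conclusions are not supported. A reader might infer that the trial will declare benefit from a time effect; the Protocol does not say it will, and it plans a direct comparison of the arms. A reader might also infer that 36 participants are too few; without a stated effect size the document does not allow that conclusion. The change is worth making before analysis, but its absence does not invalidate the trial.

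**What to change.** In sections 4.1 and 4.2 (Study 1):

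1. Replace the treatment test of the 2×4 ANOVA with one repeated-measures model that has baseline as a covariate and weeks 3, 6 and 12 as outcomes.
2. Name the **group effect**, the adjusted between-arm difference averaged over the three post-baseline visits, as the treatment test. In this model a constant benefit appears in the group term; group by visit asks only whether the benefit varies over time and should be used for nothing else.
3. If the four-level ANOVA is kept, name the **group-by-time interaction** as the treatment test instead, accepting that at low visit correlation it has less power than the group term.
4. Make the post-hoc comparisons between arms at each visit, with Holm adjustment.
5. Report time effects and within-arm changes as descriptive only.

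The cost is revised wording and a little more analysis work. No new data or participants are needed.
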